### 3.2 Primary Study Endpoint

For the primary objective (*safety of the implantation procedure: the OxyChip itself and removal of the OxyChip is expected to be well-tolerated with minimal risk for complications*). The primary endpoints will be

all grade 3 or higher toxicities according to the Common Terminology Criteria for Adverse Effects (CTCAE) that are attributed to the device or procedure.

### **3.3 Secondary Study Endpoint**

*For the secondary objective (feasibility of repeated oxygen measurements in tumors using the OxyChip and EPR oximetry) the secondary endpoint is completion of planned oxygen measurements.*

## **4 Subject Selection and Withdrawal**

### **4.1 Inclusion Criteria**

1. Phase 1A: Any tumor identified by imaging or physical exam to be accessible to OxyChip implantation and measurements and that is going to receive surgical resection with intent to remove the entire tumor. The tumor must be sufficiently large to accommodate the OxyChip.
2. Phase 1B: Any biopsy-proven malignancy expected to undergo neoadjuvant chemotherapy or radiotherapy prior to resection. The tumor must be sufficiently large to accommodate the OxyChip.
3. The tumor must be within 3 cm of the surface of the skin or mucosa.
4. Age  $\geq$ 18 years old.
5. Subject must be capable of giving informed consent
6. Anticipated time between implantation and planned surgical excision of at least three days.
7. Tumors must be  $\geq$  2.5 cm in minimum diameter to be eligible.

### **4.3 Subject Recruitment and Screening**

Patients will present to one of the DHMC surgical, medical or radiation oncologists who will review the case. If the patient meets criteria for enrollment and the surgeon is planning tumor resection, the case will be reviewed with the PI or a co-investigator to determine suitability for enrollment. The patient will then be recruited and consented by the PI or one of the co-investigators in collaboration with the treating surgical, medical or radiation oncologists.

Patient enrollment will be entered into the Velos eResearch Database.

The study will not be advertised.

Screening requirements for the study:

1. Any imaging of the tumor (including ultrasound, MRI or CT scans) must be available for review to guide the OxyChip implantation. A radiation-therapy-planning CT scan may be used to meet this requirement in Phase 1B. For patients with tumors involving the skin, which are easily visualized and palpated on clinical exam, imaging is not required. This requirement will be determined by PI and surgical oncologist, but in general, will be consistent with standard practice for surgical planning for each tumor.
2. Physical examination.
3. Pregnancy test, if applicable, within 14 days of OxyChip implantation.

### **4.4 Early Withdrawal of Subjects**

#### **4.4.1 When and how to withdraw subjects**

A subject may be withdrawn from the study at any time at the discretion of the treating physicians or if the patient withdraws consent. If the OxyChip was placed before withdrawal, there will be two options for withdrawing from the study, as follows:

1. Discontinuing the oxygen measurements: Repeated oxygen measurements will be stopped at the patient's request for any reason. The reason will be recorded and tracked as part of the study feasibility outcome. Under these circumstances, the OxyChip will not be immediately removed. Preferably, the OxyChip will be removed at the time originally planned when the tumor is resected.
2. Removal of the OxyChip: The OxyChip may be removed at any time at the patient's request. If the patient wishes to withdraw completely from the study, then the OxyChip will be removed. The OxyChip will also be removed early if there is an adverse event associated with the implant or if it is having (or may have) an adverse effect on the patient. This will require either surgical excision of the OxyChip or an en bloc surgical resection of the tumor with inclusion of the OxyChip. The type of surgery that is performed will be at the discretion of the surgical oncologist.

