## 3 Study Design

### 3.1 General Design

This is a Phase 1 clinical trial. Total enrollment will be 60 evaluable patients. Evaluable patients will be defined as patients who have the OxyChip implantation for the minimum of 3 days.

The study is split into Phase 1A (shorter duration of implantation with no other cancer therapy planned prior to excision) and Phase 1B (longer duration of implantation that is typically up to 12 weeks while receiving radiation therapy or longer if receiving neoadjuvant chemotherapy prior to surgical excision), as described below. OxyChip implant duration for both phases can be extended to 52 weeks (excluding the initial 6 evaluable patients in Phase 1A which may have the OxyChip implanted up to 4 weeks).

[figure not shown]
The initial 6 evaluable patients in Phase 1A will have the OxyChip placed for a short duration (up to 4 weeks) after which the OxyChip will be removed when the tumor mass is resected, prior to delivery of any further therapies. After successful implantation and removal of the OxyChip without any unacceptable toxicity in the first 6 evaluable patients, the Phase 1A cohort will be expanded to a total of 30 patients. In order to complete the safety and toxicity assessment of the short-term implantations, we will require that at least 3 patients have OxyChip implantations for a duration of at least 2 weeks, prior to proceeding to Phase 1B (long term implantation). This may require enrollment of additional patients in Phase 1A in order to meet this criterion. Phase 1B will consist of one cohort of 3 evaluable patients receiving chemotherapy treatment and one cohort of 3 evaluable patients receiving radiotherapy. Only after a full evaluation of the first 3 patients that underwent chemotherapy will additional patients receiving chemotherapy be enrolled. Similarly, only after a full evaluation of the first 3 patients that underwent radiotherapy will additional patients receiving radiotherapy be enrolled. The two cohorts of 3 patients in Phase 1B are independent of each other, so either of these cohorts may continue accrual after the initial 3 patients while the other is still accruing for the initial 3 patients. A total of 30 patients will be enrolled in Phase 1B. .

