#### **4.4.2 Data collection and follow-up for withdrawn subjects**

Survival data will be collected on all patients for up to a year following implantation, including subjects withdrawn from the study following implantation. Survival data will be collected from the social security death index as well as the DHMC medical record. In addition, the reasons for early withdrawal will be collected to determine if the device or measurement procedures contributed to the early withdrawal.

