# 7 Statistical Plan

## 7.1 Statistical Methods

This is a first-in-humans pilot study/Phase I trial designed to (1) test the safety and toxicity of the OxyChip and patient tolerance of its presence and to (2) help design a larger confirmatory study. As such, the study was sequentially designed into different cohorts, as previously described in section\_3.1. The criteria for proceeding with each cohort is not based on statistical significance but on the presence and severity of any unexpected adverse events and whether they can be attributed to the OxyChip. The sample size was selected to be within the range recommended for early phase I trials.

For purposes of examining the secondary goal, the feasibility of using the OxyChip to assess PO2, we will use a qualitative assessment about whether any attempted measurements were successful, and assess the time for making measurements. Oxygen measurements will be averaged across visit days (if available) per subject for all subjects in Phase 1A and Phase 1B. We will use a paired t-test to detect statistically significant acute changes in pO2. To compare time period measurements per visit across patients, we will use an ANOVA model to account for individual variation of the baseline pO2. Finally, if the oxygen level exhibits a nonlinear pattern we will use a nonlinear fitting technique. To account for substantial variations of pO2 across patients, methods of repeated measurements and mixed modeling will be used.

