## 7.2 Subject Population(s) for Analysis

The subject populations whose data will be subjected to analysis (both primary and secondary) include all evaluable participants in this Phase I trial.

---

 US Dept of Health and Human Services, Food and Drug Administration Center for Devices and Radiological Health. Center for Biologics Evaluation and Research. "Investigational Device Exemptions (IDEs) for Early Feasibility Medical Device Clinical Studies, including Certain First in Human (FIH) Studies: Guidance for Industry and Food and Drug Administration Staff". Document issued October 1, 2013.  
<http://www.fda.gov/MedicalDevices/DeviceRegulationandGuidance/HowtoMarketYourDevice/InvestigationalDeviceExemptionIDE/ucm162453.htm>.

Browne RH: On the use of a pilot sample for sample size determination. *Stat Med.* 1995, 14: 1933-1940.

Sim J, Lewis M: The size of a pilot study for a clinical trial should be calculated in relation to considerations of precision and efficiency. *J Clin Epidemiol.* 2012, 65: 301-308.

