### 8.2 Recording of Adverse Events

Clinical study subjects will be questioned about adverse effects at study visits. The visits will be documented in the clinical records. Adverse effects with suspected causal relationship to study procedures, determined by the PI or co-I, will be recorded on study adverse effects forms and summarized in CRFs.

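### The 3-day evaluability rule takes patients whose OxyChip is removed early for an adverse event out of the primary safety analysis, even at grade 3 or higher

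*Combined protocol and SAP*

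**What the plan says.** Three provisions act together.

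- **Removal.** Section 4.4.1, item 2: "The OxyChip will also be removed early if there is an adverse event associated with the implant". It also covers a chip that has, or may have, an adverse effect on the patient. No grade is stated, and removal means surgery: excision of the chip or en bloc resection of the tumor.
- **Endpoint.** Section 3.2 counts "all grade 3 or higher toxicities according to the Common Terminology Criteria for Adverse Effects (CTCAE"), where attributed to the device or procedure. Removal of the chip is not itself listed.
- **Analysis set.** Section 3.1: "Evaluable patients will be defined as patients who have the OxyChip implantation for the minimum of 3 days". Section 7.2 says that the subject populations "whose data will be subjected to analysis (both primary and secondary) include all evaluable participants in this Phase I trial". Neither section makes an exception for a chip removed because of an adverse event.

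Other provisions bear on the point. Eligibility (Section 4.1, item 6) requires "Anticipated time between implantation and planned surgical excision of at least three days". Section 8.2 says: "Adverse effects with suspected causal relationship to study procedures, determined by the PI or co-I, will be recorded on study adverse effects forms". Under Section 4.4.2, "the reasons for early withdrawal will be collected to determine if the device or measurement procedures contributed to the early withdrawal". Section 8.4 stops the study for any grade 3 or higher toxicity and does not restrict this to evaluable patients.

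**The concern.** A minimum implantation time is a sensible condition for feasibility: a chip that was in place for one day says little about repeated oximetry. It is a poor condition for safety, because an adverse event can be the reason that the minimum was not reached. Bleeding, infection and allergic reaction at the site are on the monitoring list of Section 2.1, and Section 1.7 names bleeding and infection among the risks of implantation. Any of these could arise in the first two days.

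For a patient removed early because of an attributed grade 3 or higher event, the rule works in one direction only: an event leaves the numerator and the patient leaves the denominator, so the reported rate falls. The trial is meant to help design a larger study (Section 7.1), residence has been extended to 52 weeks (Section 1.6.2), and evaluation of permanent implantation has been permitted (Section 1.5). Readers planning that work need the early procedural and device failures in the safety result.

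**Working it through.** **1. The plan's own figures.** There is no alpha, power or event rate to reproduce; Section 7.1 takes the sample size from a recommended range for early trials. The counts agree: 6 + 24 = 30 in Phase 1A, and 30 + 30 = 60 evaluable overall. Section 7.1 plans no proportion or interval for the primary endpoint, so the intervals below are added for illustration.

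**2. Tracing the definitions.** Take a patient whose chip is removed under Section 4.4.1, item 2, for an event attributed to the device or procedure.

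| Grade of event | Time of removal | Meets 3.2? | Evaluable (3.1)? | Event counted in primary analysis (7.2)? | Stopping rule (8.4)? |
|---|---|---|---|---|---|
| 3 or higher | before day 3 | yes | no | **no** | yes |
| 3 or higher | day 3 or later | yes | yes | yes | yes |
| below 3 | before day 3 | no | no | no; patient also absent from denominator | no |
| below 3 | day 3 or later | no | yes | no; patient in denominator | no |

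The first line is the defect: the event meets the endpoint and triggers the stopping rule, yet falls outside the analysis. The last two lines depend on whether an event that leads to surgical removal can be graded below 3. That turns on CTCAE definitions that the documents do not reproduce.

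**3. Size, with assumed counts.** Exact (Clopper-Pearson) two-sided 95% limits for x events in n patients: with x = 0, the upper limit is 1 − 0.025^(1/n); with x ≥ 1, the lower limit is the 2.5% quantile of Beta(x, n − x + 1) and the upper is the 97.5% quantile of Beta(x + 1, n − x). If k patients are removed before day 3 and replaced, all implanted = evaluable + k.

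One attributed grade 3 or higher event with removal before day 3:

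- Whole trial, replaced. Section 7.2 as written: 0/60, upper limit 1 − 0.025^(1/60) = 5.96%. All implanted: 1/(60 + 1) = 1/61 = 1.6%, limits 0.04% and 8.80%.
- One 30-patient phase, replaced. As written: 0/30 (0 to 11.57%). All implanted: 1/31 = 3.2% (0.08 to 16.70%).
- Not replaced, for example because the Study Summary caps Phase 1B at 30 enrolled. As written: 0/29 (0 to 11.94%). All implanted: 1/30 = 3.3% (0.08 to 17.22%).

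The 0/60 case assumes that recruitment is completed. Section 8.4 allows re-opening only once the event is judged unrelated to the OxyChip or the oxygen measurements. An event attributed to the implantation procedure could meet that condition and still belong to the endpoint. If the study stayed closed after n implants, the contrast would be 0/(n − 1) against 1/n.

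**4. The supplementary removal row, with assumed counts.** With no grade 3 or higher event, one removal on or after day 3 would read 1/60 = 1.7% (0.04 to 8.94%). Three removals, all before day 3 and replaced, would read 3/63 = 4.8% (0.99 to 13.29%). These count a different outcome from the grade 3 or higher endpoint and stand beside it; they do not measure bias in it.

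**The case against.** The strongest reply is that such an event could hardly be missed. Effects with a suspected link are recorded whatever their grade (Section 8.2). Section 8.3.1.1 covers serious and non-serious effects and requires follow-up of associated ones. Section 2.1 lists monitored effects without a grade limit. Withdrawal reasons are collected expressly to judge the device's role. Cohort decisions rest on a clinical reading of events: "The criteria for proceeding with each cohort is not based on statistical significance but on the presence and severity of any unexpected adverse events". The cancer center's data safety monitoring committee reviews adverse device effects. The progress report in Section 1.5 goes below grade 3, giving a maximum grade of 1, which suggests that serious early events may be rare.

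All of this stands, and it rules out several stronger readings that a reader might infer:

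- *That early removals go unrecorded or cannot affect the conduct of the trial.* The provisions above say otherwise, and the stopping rule is not confined to evaluable patients.
- *That the endpoint certainly misses removals for lesser events.* If a removal-triggering event is graded 3 or higher, is attributed, and occurs on or after day 3, it is counted. The documents do not settle how such events would be graded.
- *That patients lost before day 3 are mostly those with device problems.* Eligibility makes a planned resection that early unexpected, so this is plausible. But the interval is only an anticipated one, patients may ask for removal at any time, the surgeon sets the timing of resection (Section 5.2.4), and no data are given.

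What the reply does not reach is the analysis set. Recording, oversight and stopping do not place the event in the analysis that Section 7.2 defines.

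**Conclusion.** The concern holds for the analysis set. Following Sections 3.1 and 7.2 as written, a patient whose chip is removed before day 3 for a device- or procedure-associated event is left out of the primary safety analysis at any grade. This follows from a stated rule; it is not a matter of missing detail. The effect is on the reported safety result, not on patient protection.

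The frequency cannot be derived from the documents. Under the assumption of one attributed grade 3 or higher event, one replacement and completed recruitment, the upper 95% limit moves from 6.0% to 8.8% and the point estimate from 0 to 1.6%. Because grading of removal-triggering events below 3 remains open, the count of removals is warranted only as a supplement to the endpoint.

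**What to change.** - **Section 7.2:** define the primary safety population as all patients in whom an OxyChip was implanted or implantation was attempted. Keep the 3-day evaluable definition for the enrolment target and the feasibility analysis.
- **Sections 3.2 and 7.1:** beside the grade 3 or higher toxicities, report the number and proportion (exact 95% CI) of implanted patients whose chip was removed because of a device- or procedure-associated adverse event of any grade, per phase and overall. Use the reasons collected under Section 4.4.2. Do not count resections re-timed for oncologic reasons, patient-request removals without an adverse event, or the minor-procedure removals of Section 5.2.4 (surgery unnecessary, or delayed beyond 52 weeks).

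The endpoint definition, stopping rule, removal trigger and enrolment target stay as they are. The cost is a short attribution definition, one table row from data already collected, and a safety figure that may look slightly less favourable. Changing only the denominator of the removal row would not be enough: an attributed grade 3 or higher event with removal before day 3 would still be missing from the primary result.

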#### **4.4.2 Data collection and follow-up for withdrawn subjects**

Survival data will be collected on all patients for up to a year following implantation, including subjects withdrawn from the study following implantation. Survival data will be collected from the social security death index as well as the DHMC medical record. In addition, the reasons for early withdrawal will be collected to determine if the device or measurement procedures contributed to the early withdrawal.

## **5 Study Device**

### **5.1 Description**

The device, OxyChip, used in this study is made in-house using a two-step process. In the first step, LiNc-BuO crystals are synthesized using commercially available starting materials. In the second step, the LiNc-

BuO crystals are embedded in PDMS, a biocompatible polymer. The product is made in the form of a cylindrical pellet (0.6-mm diameter and 5-mm length) for implantation.

### 5.1.1 Materials used for fabrication

LiNc-BuO crystals are synthesized using the published procedure. The method uses lithium granules, 5,9,14,18,23,27,32,36-octa-*n*-butoxy-2,3-naphthalocyanine (Nc-BuO), *n*-pentanol, *n*-hexane, and *tert*-butyl methyl ether, all purchased from Sigma-Aldrich Chemical Co (St. Louis, MO, USA). PDMS is a medical grade silastic polymer (A-103) from Factor II, Incorporated (Lakeside, AZ).

### 5.1.2 Synthesis of LiNc-BuO crystals

Lithium granules (0.0053 g, 0.774 mmol) are added to *n*-pentanol (15 ml) and refluxed for 30 min under nitrogen atmosphere. The mixture is cooled to room temperature and Nc-BuO (0.1 g, 0.0774 mmol) is added and refluxed gently for 2.5 hours under nitrogen atmosphere. After cooling down to room temperature, 300 ml of *tert*-butyl methyl ether is added and filtered through a small silica gel plug. The solvent is then evaporated under reduced pressure to 3 ml of solution. The concentrate is dissolved in 100 ml of *n*-hexane. The greenish solution is slowly evaporated under reduced pressure to yield shiny crystals of lithium 5,9,14,18,23,27,32,36-octa-*n*-butoxy-2,3-naphthalocyanine (LiNc-BuO). The crystals are washed with methanol and dried under a vacuum. Please see **Attachment 2** for details of LiNc-BuO synthesis.

### 5.1.3 Method for fabrication of OxyChip

OxyChips are fabricated by cast-molding and polymerization, as reported. The silastic polymer is mixed at the recommended base-to-crosslinker ratio (10:1), and crystals of LiNc-BuO are thoroughly dispersed into this mixture using a spatula. The base-crosslinker/LiNc-BuO microcrystal mixture is poured into a polystyrene weighing boat and degassed under vacuum. The degassed mixture is cured in an oven at 70°C for 3.5 hours. Please see **Attachment 2** for details of SOP for fabrication of OxyChips.

### 5.1.4 Sterilization

As a “critical device” (*i.e.*, a device that is introduced into a sterile area of the body), each OxyChip is sterilized with a SAL of 10^-6 and validated as per the published standard (Sterilization of health care products – Moist Heat – Part 2: Guidance on the application of ANSI/AAMI/ISO 17665-1; TIR17665-2:2009). The sterilization procedure is performed by trained staff, using the clinical autoclaves and standard procedures. Sterilizations are recorded. Individual OxyChips devices are placed in sealable autoclave bags with process indicators and are labeled with product identification number. The steam sterilization is done in the autoclave at gravity cycle (at 121°C (249.8°F)) and 15 PSIG for 30 minutes. The sterilization cycle is validated using biological indicators (BI) and chemical indicators (CI). If the indicator results are appropriate, the implant is released for use. The implant will remain sterile in storage as long as the integrity of the package is maintained. Importantly the device chemistry (PDMS and LiNc-BuO) is stable under high temperature conditions. (See Standard Method 67.0 for further details.)

### 5.1.5 Calibration of oxygen sensitivity

[figure not shown]
Prior to autoclaving, each OxyChip is calibrated. Each chip is placed individually in a 5-mm diameter NMR tube (Norell) modified for gas delivery. A calibration line is generated using the measured linewidths collected from an L-band EPR spectrometer under known conditions. EPR Linewidths are plotted relative to the % oxygen exposure to obtain the calibration curve, which is used to calculate pO2 from the measured linewidths using the corresponding samples implanted within the tumors. In addition, after each chip is implanted and subsequently excised along with the tumor, the OxyChip is re-calibrated and the pre- and post-implants are compared.

